We will also evaluate the neurobiological mechanisms involved in the antidepressant response to AV-101. We expect that this effect may modulate glutamate transmission and reverse the clinical symptoms of depression. The demonstration that a glycine-antagonist produces antidepressant effects without psychotomimetic side effects would support the therapeutic relevance of the glycine site of the NMDAR and could direct the development of novel drug targets for the treatment of depression.

b. Design

Male and female patients, ages 18 to 65 years, with a diagnosis of MDD, currently in an episode of major depression, will be recruited for this study. This study will consist of a randomized, double-blind crossover administration of either the glycine receptor antagonist AV-101 (1,080 or 1,440 mg/day given orally) or placebo for 2 weeks. The study will assess the efficacy in improving overall depressive symptomatology and tolerability of AV-101 in treatment-resistant MDD. Other aims of the study include: 1) determining whether changes in brain neurochemicals (e.g. glutamate) and peripheral biomarkers obtained via MRS and cerebrospinal fluid (CSF) correlate with antidepressant response (decrease in Hamilton Depression Rating Scale (HDRS) total scores) to AV-101 in patients with treatment-resistant MDD, and 2) examine other potential biomarkers of response.

c. Outcome Measures

Primary: Hamilton Rating Scale (HDRS) total score.

PI name: [name]
Protocol number: 15-M-0151

Version: Am C

Secondary: Proportion of subjects achieving remission (HDRS \leq 7) and response (\geq 50% reduction from baseline in HDRS total score); change from baseline in Hamilton Anxiety Rating Scale (HAM-A), Montgomery-Asberg Depression Rating Scale (MADRS), and the Columbia Suicide Severity Rating Scale (C-SSRS) total scores. Surrogate biomarkers of drug effect/response include: changes in prefrontal glutamate levels measured with 7T 1 H-MRS.

PI name: [name]
Protocol number: 15-M-0151

Date: 05-15-18
Version: Am C

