2. STATISTICAL ANALYSIS

a. Analysis of data/study outcomes

The double blind will be broken and the randomization status of each participant will be revealed only after the completion of this study in all 20 individuals. An interim **blinded** analysis may be performed no more than one time (for example, at the request of the PI's Board of Scientific Counsellors) to inform ongoing scientific efforts and productivity of the Branch; however, this interim analysis will not serve as the basis for decisions to change study procedures or to terminate the study. (**Specific Aim 1**) To assess the efficacy of AV-101 compared with placebo in improving overall depressive symptomatology over a two-week course of treatment in patients with treatment-resistant MDD currently experiencing a major depressive episode.

The primary aim will be accomplished by assessing the efficacy of two weeks of oral AV-101 (1,080 or 1,440 mg/day) compared with placebo in improving overall depressive symptomatology. The primary assessment of efficacy is a comparison of HDRS scores between treatment groups.

The difference between AV-101 and placebo will be examined using a linear mixed model with restricted maximum likelihood estimation where drug and time are within subjects factors. Drug and time main effects and their interaction will be included in the model as within subjects factors. Baseline scores for each phase will be used as a time-dependent covariate. A random intercept and subject effect will be included if they contribute significantly to the model. Schwarz's Bayesian criteria will be used to examine the most appropriate covariance structure prior to formal analyses, where a compound symmetry structure will be used in another is not preferred. Bonferroni corrected post hoc tests will be used to follow up on a significant drug by time interaction. Cohen's d will be calculated to describe the effect size.

Additional follow-up analyses may examine the potential for carryover effects within the crossover study. First, an additional phase variable may be added to the original statistical model. Second, results in the first phase of the study may be examined separately to understand whether any drug effect remains in a parallel-like design.

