Secondary analyses will be conducted in the same manner for BPRS, CADSS, C-SSRS, HAM-A, MADRS, PANAS, SHAPS, SSI, TEPS, and YMRS. A similar statistical model will be used to examine secondary measures. Bonferroni-like corrections will be used to determine the significance of secondary analyses.

Criteria for significance

Significance will be evaluated at p<.05, two-tailed.

Analyses will be based on the intent-to-treat (ITT) principle where all randomized subjects who receive baseline and at least one post-baseline assessment will be included. A subject will be considered a responder if the HDRS total score has decreased by 50% or more from baseline to endpoint. Response rates will be analyzed using McNemar's test for repeated measures categorical outcomes.

Safety and tolerability assessments will be based on the safety analysis set which will include all randomized subjects who are given study treatment.

The incidence rate of adverse events will be tabulated by preferred term and system organ class; serious adverse events, adverse events leading to death, and adverse events leading to withdrawal of subjects will be tabulated for each treatment group.

Analyses of surrogate neurobiological markers

Multiple logistic regression models (for categorical outcome, response vs. non-response) will evaluate candidate biological markers for independent association with outcomes. For these models, we will compute robust standard errors or associated 95% confidence intervals.

PI name: [name]
Protocol number: 15-M-0151

Date: 05-15-18
Version:Am C

b. Power analysis

Previous studies by our group (see **Background**) demonstrated improvement in depression at 72 hours with an effect size of d=0.67. Assuming α =.05, two-tailed, 20 patients with MDD would provide 81% power to detect an effect of the same size as previously reported with a double-blind crossover study. We are primarily interested in detecting drugs with a large effect size that occurs within a short period of time (\leq 72 hs) as there are already many antidepressants with small effect sizes after 2 weeks of treatment. This is the reason for not studying a much larger number of patients; in addition, the current study design uses a crossover design.

c. Accrual number

If we assume that 20% of subjects will either not complete the drug free period or will drop out during the crossover double-blind portion of the study, then 25 MDD patients need to be recruited.

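### The undefined Bonferroni-like correction also covers BPRS, CADSS and YMRS, where the question is harm, and so makes a true worsening harder to detect than an uncorrected test would

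*Combined protocol and SAP*

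**What the plan says.** Section 2.a (Analysis of data/study outcomes) states: "Secondary analyses will be conducted in the same manner for BPRS, CADSS, C-SSRS, HAM-A, MADRS, PANAS, SHAPS, SSI, TEPS, and YMRS". It then adds: "Bonferroni-like corrections will be used to determine the significance of secondary analyses". No divisor, procedure or family is given, and no scale is exempted. The significance criterion is 0.05 two-sided, without saying whether that is per test or familywise.

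Because the secondary scales follow the primary model, its follow-up rule appears to carry over as well: "Bonferroni corrected post hoc tests will be used to follow up on a significant drug by time interaction".

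Section 1.c (Outcome Measures) gives a different secondary list: remission, response, HAM-A, and "Montgomery-Asberg Depression Rating Scale (MADRS), and the Columbia Suicide Severity Rating Scale (C-SSRS) total scores". BPRS, CADSS and YMRS are not in it, so the two lists do not settle what the family is.

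On harm, section 1.a (Objective) hopes to show that a glycine antagonist "produces antidepressant effects without psychotomimetic side effects". Section 1.b (Design) adds: "The study will assess the efficacy in improving overall depressive symptomatology and tolerability of AV-101 in treatment-resistant MDD". The safety text in section 2.a says only this about how safety data will be summarised: "The incidence rate of adverse events will be tabulated by preferred term and system organ class". It assigns no rating scale to the safety analyses.

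Section 2.a also names two populations. For the efficacy-type analyses, "all randomized subjects who receive baseline and at least one post-baseline assessment will be included". Safety and tolerability are to use a safety set of all randomised subjects who received study treatment.

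**The concern.** A familywise correction guards against claiming a benefit that is not there. On a scale where the worry is harm it works the other way: it raises the evidence needed before a worsening is called significant. BPRS and CADSS bear on the stated interest in avoiding psychotomimetic effects, and YMRS bears on tolerability. Grouping them with scales such as PANAS, SHAPS and TEPS means that the threshold for a harm signal depends on how many unrelated scales were also collected.

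Since the family is not stated, two statisticians following this plan could give different verdicts on the same BPRS or CADSS result. Dropping the correction would not be enough either: with 20 patients, an uncorrected non-significant result still leaves appreciable worsening possible. A confidence interval shows how much, and the plan specifies none for these scales.

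**Working it through.** **Inputs.** From section 2.b (Power analysis): n = 20 in a crossover, d = 0.67, two-sided 0.05, stated power 81%. From section 2.a: ten secondary scales. Assumed, because the documents give no figure: the effect size on BPRS, CADSS and YMRS (0.67 is borrowed from the efficacy calculation), the family size m, the number of time points k and the correlation ρ between them. A single paired t-test stands in for the planned mixed model.

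**Formula.** Power = P(|T| > c), where T is noncentral t with df = 19 and noncentrality d√n, and c is the two-sided critical value at α = 0.05/m.

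**The plan's own figure.** d√n = 0.67 × √20 = 2.996 and c = 2.093, so power = 81.1%. The stated 81% is reproduced.

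**Same effect, plain Bonferroni:**

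| Tests m | α per test | c | Power, 0.5 SD | Power, 0.67 SD | Power, 1.0 SD |
|---|---|---|---|---|---|
| 1 | 0.05 | 2.093 | 56% | 81% | 99% |
| 3 | 0.0167 | 2.625 | 37% | 65% | 96% |
| 10 | 0.005 | 3.174 | 21% | 45% | 88% |

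The worsening detectable with 80% power rises from 0.66 SD (m = 1) to 0.78 SD (m = 3) and 0.91 SD (m = 10). With a step-down procedure the threshold for a given scale lies between 0.05/m and 0.05, so the loss is smaller but is never a gain.

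**Sustained effect.** The planned model also has a drug main effect, which averages over time points. If 0.67 SD is the effect at every one of k time points, with equal correlation ρ, the effect on the averaged contrast is 0.67 / √[(1 + (k − 1)ρ)/k].

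| k | ρ | Averaged effect (SD) | Power, m = 1 | Power, m = 10 |
|---|---|---|---|---|
| 3 | 0.7 | 0.67/0.894 = 0.75 | 89% | 58% |
| 3 | 0.3 | 0.67/0.730 = 0.92 | 97% | 81% |
| 5 | 0.7 | 0.67/0.872 = 0.77 | 90% | 61% |
| 5 | 0.3 | 0.67/0.663 = 1.01 | 99% | 89% |

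So ten-test power is 58–89%, against 89–99% uncorrected. The 45% applies only when 0.67 SD is already expressed in the SD of the contrast that is tested.

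**What an interval would show.** The 95% half-width is 2.093/√20 = 0.468 SD of the paired contrast. With an observed difference of exactly zero, a worsening of up to 0.47 SD is not excluded.

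**Cost in false signals.** With no true effect, three independent scales and one two-sided test each, the chance of at least one significant worsening is 1 − 0.975³ = 0.073 uncorrected. Under a ten-test Bonferroni it is 1 − 0.9975³ = 0.0075.

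**The case against.** Every multiplicity correction costs power, and this one changes only significance labels. Estimates and adverse event tables are the same either way, and so, in all likelihood, is Cohen's d. The documents do not call BPRS, CADSS or YMRS harm scales, and for YMRS the only textual support is the mention of tolerability. The power analysis points to a Background section that is not in the available text, so roles for these scales could be stated there. The 45% depends on a borrowed effect size and a simplified test. These points stand, and they limit the finding to a modest one.

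Two further objections also stand and shape the remedy. C-SSRS and SSI sit in the same corrected list, and the same argument could be made for them. Also, if these scales are tolerability measures, section 2.a names a safety set that differs from the efficacy population, and the two need to be reconciled.

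Two stronger readings are tempting. A reader might infer that the correction across scales multiplies with the post hoc correction across time points, which would give much lower power. The text does not say that the two are combined, and a worsening could also show in the drug main effect or in the interaction test itself. A reader might also infer that the sponsor will take a non-significant result on these scales as evidence of no harm. Nothing in the documents says so.

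**Conclusion.** The point holds as a cheap improvement. As written, the correction reaches scales on which the question is harm, and against an uncorrected test it can only reduce the chance of detecting a true worsening. On the paired-t illustration the loss runs from about 16 points (81% to 65%, three tests) to about 36 points (81% to 45%, plain Bonferroni over ten). It is smaller under a step-down method or, at most of the settings tried, for an effect sustained over time. The size rests on an assumed effect and an unstated family; the direction does not. Treating the three scales as harm-oriented is general knowledge, supported for BPRS and CADSS by the psychotomimetic rationale and more weakly for YMRS by the tolerability aim.

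It would be wrong to infer any threat to the main result. The primary HDRS comparison and the adverse event tabulations do not depend on this rule.

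**What to change.** Amend the SAP wording as follows.

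- **Correction.** Limit it to a named list of efficacy secondaries, state whether response and remission belong to that list, and name the procedure.
- **BPRS, CADSS and YMRS.** Analyse them outside that family with the planned mixed model. For each, report the AV-101 minus placebo drug main effect with an unadjusted 95% confidence interval as the single headline contrast. State the limit on the worsening side as the worsening not excluded.
- **Time points.** Give the differences with descriptive intervals whether or not the interaction is significant.
- **C-SSRS and SSI.** State on which side they fall. If they stay in the efficacy family, report their unadjusted intervals as well.
- **Population.** Reconcile it with the safety set: model all treated subjects who have a baseline and at least one later score, and report how many treated subjects do not.

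This needs no new data, visits or patients. The price is the rise in false safety signals from about 0.7% to about 7%, under the assumptions shown. Reading every time-point interval as a test would push that higher, which is why they should be labelled descriptive.

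### McNemar's test for response ignores phase and randomised sequence; Prescott's test in the same form is a cheap improvement for this secondary endpoint

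*Combined protocol and SAP*

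**What the plan says.** The Précis (Outcome Measures) lists response and remission among the secondary outcomes: "Secondary: Proportion of subjects achieving remission", followed by response. Section 2a (Criteria for significance) defines response: "A subject will be considered a responder if the HDRS total score has decreased by 50% or more from baseline to endpoint". It then fixes the test: response rates "will be analyzed using McNemar's test for repeated measures categorical outcomes". It does not say whether this is the exact, mid-p or asymptotic version, and it names no test for remission specifically.

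Phase appears in section 2a in two other places. Phase-specific baselines enter the linear mixed model as a covariate. As an optional carryover follow-up, "an additional phase variable may be added to the original statistical model"; that model is the HDRS mixed model. Nothing equivalent is given for the binary comparison. The documents do not state the allocation between the two sequences, the expected response rates, or any expected phase difference.

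**The concern.** In a two-period crossover, each patient who responds in only one phase is a discordant pair. McNemar's test asks whether these pairs favour AV-101 or placebo, and treats a pair from an AV-101-first patient exactly like one from a placebo-first patient. If patients tend to do better in one phase whatever they take, some discordant pairs reflect phase, not drug. With equal sequences those pairs fall on both sides and dilute the comparison. With unequal sequences they fall more on one side and push the comparison in that direction. The sequence is known for every patient, so this can be avoided. At stake is the efficiency and fairness of a named secondary comparison in a trial of 20 patients.

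**Working it through.** **The plan's own figures.** For d = 0.67, 20 patients and two-sided 0.05, the paired t-test has noncentrality 0.67 × √20 = 3.00 on 19 degrees of freedom, which gives 81.1% power. The stated 81% reproduces. Recruitment is 20/(1 − 0.20) = 25, also as stated. Neither figure concerns response, for which no power is given.

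**Inputs.** From the documents: 20 completers, crossover, two-sided 0.05. Assumed, because the documents give none: response of 50% on AV-101 and 20% on placebo; a latent normal model with within-patient correlation 0.3; a phase shift of 0, 0.5 (moderate) or 1.0 (large) on the probit scale, split as plus and minus half around the mean, with better response in phase 2. At a 30% mean, the moderate shift is about 22% v 39% by phase and the large one about 15% v 49%.

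**Tests.** Let *b* be the number who respond on AV-101 only and *c* the number on placebo only.
- McNemar, exact: p = 2 × P(Bin(b+c, ½) ≤ min(b, c)). Asymptotic: (b − c)²/(b + c) against chi-squared on 1 df.
- Prescott: for each patient take D = phase 2 response − phase 1 response (−1, 0, +1) and compare D between the randomised sequences. The exact form conditions on the total numbers of −1, 0 and +1 and permutes sequence membership. Patients with D = 0 stay in.

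**Why imbalance biases McNemar.** With no drug effect and phase response rates q1 and q2, the expected value of b − c is (placebo-first − AV-101-first) × (q2 − q1). At 10/10 this is 0. At 8 AV-101-first and 12 placebo-first with the moderate shift it is 4 × (0.39 − 0.22) = +0.68 pairs towards AV-101; at 12/8 it is −0.68. In Prescott's comparison the phase effect is common to both sequences and cancels whatever the split.

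**Power at 10/10, two-sided 0.05, by enumeration of all outcome tables:**

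| Phase shift | 0 | 0.5 | 1.0 |
|---|---|---|---|
| McNemar exact | 42.3% | 37.9% | 26.5% |
| Prescott exact | 42.7% | 40.5% | 35.8% |
| Gain (points) | +0.4 | +2.6 | +9.3 |
| McNemar asymptotic | 55.1% | 50.2% | 37.2% |
| Prescott asymptotic | 55.7% | 54.4% | 50.9% |
| Gain (points) | +0.6 | +4.2 | +13.7 |

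A second model (logistic, patient SD 1 on the logit scale, phase odds ratio 1 / 2 / 4 / 8) shows the same pattern. Exact: McNemar 41.3 / 39.1 / 33.0 / 24.2% v Prescott 41.8 / 40.6 / 37.8 / 34.1%. Mid-p: 52.9 / 50.6 / 44.0 / 34.2% v 53.4 / 52.2 / 49.5 / 46.0%.

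**Power at unequal sequences, moderate shift, exact tests.** McNemar: 47.8% at 8/12 and 28.9% at 12/8. Prescott: about 39 to 40% at either split when the two-sided p-value is twice the smaller tail, and about 45% at either split when it sums all outcomes no more likely than the one observed. The convention matters when sequences are unequal and should be stated.

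**Cost if there is no phase effect.** At 10/10, exact Prescott against exact McNemar is 16.2% v 17.0% at alpha 0.01, with a loss of about 1 point at 0.025 also. At stricter levels the loss is a little larger: 8.5% v 10.7% at 0.005, and 8.1% v 10.6% at 0.05/12. At 8/12 the loss reaches about 4 points, depending on form and alpha.

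**Type I error (30% response on both treatments).** At 10/10, asymptotic McNemar is at 4.6 / 3.7 / 2.0% for the three shifts, so it is not inflated. Asymptotic Prescott is at 4.3 to 4.5% at 10/10 and at most 5.1% at 8/12.

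**The case against.** The strongest objection is that the plan does not say which McNemar test it means. If it is the asymptotic one, exact Prescott looks worse: 42.7% v 55.1% with no phase effect, about 12 points. But that gap comes from setting an exact test against an asymptotic one, not from using sequence. Matched form for form at 10/10, Prescott is level or ahead. What stands is that the form must be stated and kept the same.

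Three other points stand in part:
- The plan applies Bonferroni-like corrections to secondary analyses without saying over how many tests. At corrected levels exact Prescott gives up 1 to 2.5 points at 10/10 if phase has no effect.
- The benefit depends on a phase effect for which the documents give no evidence. The moderate shift yields only about 3 to 4 points.
- McNemar's test is a conventional paired test for a small proof-of-concept crossover.

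A reader might infer that a sequence-based exact test can never lose, or that any phase difference weakens McNemar's test. Neither follows. The Mainland-Gart exact test, which also uses sequence, loses 2.6 to 16.9 points against exact McNemar at 10/10 with no phase effect. And at 8/12 a moderate phase effect raises exact McNemar's power from 42.3% to 47.8%. That rise is bias towards AV-101, and it reverses at 12/8.

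A reader might also infer that the planned test produces false positives. At equal sequences it does not. Asymptotic McNemar reaches 5.8% at 13/7 with the large shift and about 7 to 10% at 14/6 with strong phase effects, so inflation needs marked imbalance.

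**Conclusion.** The point holds as a cheap improvement to a secondary analysis. The planned test for response takes no account of phase or sequence, and the optional phase variable in the HDRS mixed model does not repair that. If phases differ, the test loses power at equal sequences and is biased at unequal ones. Since the plan expects 20% loss and states no sequence allocation, exact balance among completers is not assured.

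For 50% v 20% response at 10/10 and alpha 0.05, a like-for-like Prescott test gains about 3 to 4 points at a moderate and 9 to 14 points at a large phase effect, and matches McNemar with none. Its price with no phase effect is about 1 point at alpha 0.025 or 0.01 for the exact form (2 to 2.5 at stricter levels), and up to about 4 points at 8/12.

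The response rates, correlation, phase shifts and sequence splits are all assumed. Neither test deals with carryover. A reader might infer that the trial's main conclusion is at risk; the documents do not support that, since the primary analysis is the HDRS mixed model and is unaffected.

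**What to change.** Before the blind is broken, amend section 2a (Criteria for significance):
- Name Prescott's test (trend test of the within-patient phase difference in response, −1/0/+1, by randomised sequence) as the test for response, and use it for remission too.
- State its form (exact, mid-p or asymptotic), choosing the form that would have been used for McNemar's test, and how the two-sided p-value is formed.
- State the planned sequence allocation, and report the number of completers per sequence.
- Keep McNemar's test as a supportive analysis.

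The cost is a few sentences and a few lines of code, with no extra patients or data, plus the small power loss given above if phase turns out to have no effect. Fixing the choice now avoids choosing the test after the phase effect by sequence has been seen.

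### The first biomarker aim concerns the continuous HDRS decrease, but the only written marker–outcome analysis is logistic regression on yes/no response in about 20 patients

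*Combined protocol and SAP*

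**What the plan says.** Section 1.b (Design) lists two biomarker aims. The first is whether changes in brain neurochemicals and peripheral biomarkers "correlate with antidepressant response (decrease in Hamilton Depression Rating Scale (HDRS) total scores) to AV-101". The second is to "examine other potential biomarkers of response". Section 1.c (Outcome Measures) names one surrogate marker: "changes in prefrontal glutamate levels measured with 7T" proton spectroscopy.

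Section 2.a, under the heading on surrogate neurobiological markers, gives the analysis: "Multiple logistic regression models (for categorical outcome, response vs. non-response) will evaluate candidate biological markers for independent association with outcomes". It adds: "For these models, we will compute robust standard errors or associated 95% confidence intervals". The outcome is defined under Criteria for significance: "A subject will be considered a responder if the HDRS total score has decreased by 50% or more from baseline to endpoint".

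The text states no expected response rate, no limit on markers per model, no fallback if a model cannot be fitted, and no power for this aim.

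**The concern.** The first biomarker aim equates antidepressant response with the size of the HDRS decrease. The written analysis replaces that size with a yes/no indicator, so a patient who improves by 49% counts the same as one who does not improve, and one who improves by 51% the same as one who remits. The second aim can reasonably take a binary outcome. The first has no analysis that matches it.

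Three consequences follow in a trial of 20:

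- Power for the mechanism question falls below what the same data allow, and a null result could come from the cut-point.
- Multiple logistic regression can separate the data perfectly and return no finite estimate. The risk grows with fewer responders and more markers, and the plan limits neither.
- The type of robust standard error is not stated, and the choice matters at this sample size.

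**Working it through.** **The plan's own figure.** Section 2.b gives n = 20, d = 0.67, two-sided α = 0.05 and 81% power for the crossover drug effect. A paired t-test has noncentrality 0.67 × √20 = 2.996 on 19 df, giving 81.1%. Accrual: 20 / (1 − 0.20) = 25. Both reproduce, but neither concerns the markers.

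**Inputs for the marker question.** From the documents: n = 20, α = 0.05 two-sided, responder = HDRS decrease of at least 50%. Assumed, because the documents give none: true correlation r between marker change and HDRS decrease of 0.4 or 0.6, response rate p of 20, 30 or 50%, and 1 to 5 markers per model.

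**Hand approximation, one marker.** By Fisher's z, power ≈ Φ(atanh(r)·√(n − 3) − 1.96).

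- r = 0.6: 0.693 × 4.123 = 2.858; Φ(0.898) = 82%.
- r = 0.4: 0.424 × 4.123 = 1.747; Φ(−0.213) = 42%.

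Cutting a normal outcome at upper proportion p shrinks the correlation by φ(z_p)/√(p(1 − p)). That factor is 0.700, 0.759 and 0.798 at p = 20, 30 and 50%.

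- r = 0.6 becomes 0.420, 0.455, 0.479; power about 45, 53, 58%.
- r = 0.4 becomes 0.280, 0.303, 0.319; power about 22, 25, 28%.

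**Simulation, 3,000 runs per cell (Monte Carlo SE at most 0.9 points).** Standard-normal markers; HDRS decrease = r × first marker + normal noise. The linear t-test is compared with a logistic Wald test using uncorrected (HC0) robust errors. A failed fit counts as no rejection.

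| Setting | Linear | Robust logistic |
|---|---|---|
| 1 marker, r = 0.4 | 43–45% | 24–26% |
| 1 marker, r = 0.6 | 83–84% | 44 / 48 / 54% |
| 2 markers jointly, r = 0.6 | 81% | 41 / 46 / 50% |
| 2 markers, inter-correlation 0.5, r = 0.6 | 69–72% | 34–42% |
| HDRS-like scores, baseline-adjusted linear, r = 0.4 | 39–40% | 22–24% |
| HDRS-like scores, baseline-adjusted linear, r = 0.6 | 80–82% | 42–50% |

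Triplets are for 20 / 30 / 50% responders. The HDRS-like rows assume baseline about N(21, SD 4), change SD 7, rounded scores, and response as a reduction of at least 50%.

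**Does the choice of logistic test explain the gap?** Only in part. For r = 0.6 and one marker, a likelihood-ratio test, which the plan does not name, gives 48 / 60 / 66%. A separate 2,000-run simulation with the ordinary model-based Wald test gives 15–41% over response rates of 20–50%. Linear regression leads in each case.

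**No finite logistic estimate, r = 0.6** (separation confirmed by linear programme, or only one outcome class):

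| Markers | 20% | 30% | 50% responders |
|---|---|---|---|
| 1 | 5.5% | 1.7% | 0.5% |
| 2 | 12.0% | 4.1% | 1.5% |
| 3 | 22.2% | 8.9% | 3.2% |
| 5 | 50.7% | 29.8% | 18.5% |

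With responders fixed at 4, 6 or 10 of 20, the rates are lower: 2.1 / 0.5 / 0.2% for one marker, 13.7 / 6.2 / 2.9% for three, 41.0 / 23.3 / 14.0% for five.

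**False positives at nominal 5% (r = 0).** HC0 logistic: 9.4 / 7.0 / 4.4% with one marker, 8.7 / 8.4 / 8.0% with three. Linear: 4.7–5.5%. Firth-penalised logistic (1,200 runs, one and three markers): 3.3–4.8%, with power at r = 0.6 and one marker of 42 / 56 / 56%.

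**The case against.** - **The plan may already cover this.** The logistic sentence is qualified as applying to a categorical outcome and ends with a plural, which could be the remnant of a plan that also had a continuous model. Section 2.a also extends a similar mixed model to secondary measures, and glutamate is listed among those in section 1.c. But no continuous marker–outcome model is written, and a mixed model for glutamate would test the drug's effect on glutamate, not its association with HDRS change. The mismatch remains. The Background section cited in 2.b is not in the text available, so this holds for the text at hand.
- **The simulation favours linear regression.** Data were generated as normal and exactly linear, and no threshold-type relation was tried. Separated fits counted as non-significant; counting them as evidence in a likelihood-ratio test raises 48 / 60 / 66% to 53 / 61 / 66%. This limits precision but does not reverse the direction.
- **Multiplicity.** The plan's Bonferroni-like correction for secondary analyses is not in these figures. With 2, 3 or 5 tests, linear power at r = 0.6 falls from 84% to 75, 70 or 62%, and at r = 0.4 from 43% to 32, 26 or 20%. This stands, but the same correction would also apply to logistic tests.
- **Robust errors.** The plan does not name HC0, and HC0 is not anti-conservative with one marker at 50% responders (4.4%). The firm point is that the type is unstated; inflation depends on the setting.
- **Fit failure.** The largest rates need five joint markers and few responders, neither of which the plan states.
- **Placebo phase.** AV-101-phase change alone cannot separate drug-related from non-specific improvement. That limits interpretation, although it follows the aim's wording about response to AV-101.

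**Conclusion.** The concern holds. As written, the first biomarker aim would be answered with an outcome that does not match it. Under the assumed normal, linear relation at n = 20, the one-marker power cost is about 30 to 40 points at r = 0.6 (84 − 54 = 30; 84 − 44 = 40) and nearly 20 points at r = 0.4 (43 − 24 = 19). Fit failure is a conditional risk: rare with one marker at 30–50% responders, substantial with few responders or several joint markers. Correlations, response rates and marker counts are assumptions, but the linear model led in every power setting tried. Linear regression does not make the aim well powered at r = 0.4. The matter should be corrected, but it does not affect the primary efficacy analysis or the sample size.

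**What to change.** In section 2.a, for the first biomarker aim:

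1. Make the main analysis a linear regression of continuous HDRS change in the AV-101 phase on marker change. Adjust for that phase's baseline HDRS, consistent with the primary model ("Baseline scores for each phase will be used as a time-dependent covariate").
2. Use t-based or small-sample-corrected intervals, and name the method.
3. Test prefrontal glutamate first, as the marker named in section 1.c.
4. To keep the question of independent association, allow a small joint linear model and state the maximum number of markers. Two is an example; the number is a judgement. State how the multiplicity correction applies.
5. Keep logistic regression on response as supportive, for instance for the second biomarker aim, using a penalised (Firth) or exact method.

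The cost is SAP wording; no new data are needed. The responder odds ratio would no longer be the headline marker result, and a slope is less familiar clinically than response. The change is best made before unblinding, so that the form of the outcome is not chosen after results are known.
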